7.3 External validity

De-identified and aggregated data for the complete Swedevox LTOT cohort for same time period (date of first to last patient randomized), in total and per participating unit will be compared regarding:

1. Proportion of randomized patients
2. Baseline characteristics

A table with baseline characteristics such as age, gender, smoking, BMI etc. will be constructed and proportion randomized patients among these will be presented.

7.4 Adherence

Completed randomized treatment or reason for not completing randomized treatment will be presented as total number and percentage, by randomized treatment, for the ITT and subgroup populations. Any loss to follow-up for the composite endpoint of death or 1st hospitalization will be presented as patient listings. For statistical analyses of outcomes, the total number of patients with data for the analysis will be tabulated in the descriptive statistics for the outcome in question. The report will contain sufficient information to construct a CONSORT diagram. (Table 1 and Table 9)

Duration of treatment (number of days during the study) will be presented descriptively by randomized group using mean, SD, median, IQR, min and max value for observed cases, in the ITT and subgroup population. (Table 8)

Self-rated hours of oxygen utilization can be given as a point estimate or an interval estimate by the patient in the 3- and 12-month questionnaires. The midpoint will be used in the analyses when interval estimates are given. For the PP analysis of the primary endpoint, the 3-month observation of self-reported oxygen utilization will be used if the 12-month observation is missing.

7.5 Analysis of primary variable

The primary endpoint of the composite event of death or 1st hospitalization at 1 year (day 365; day 0 being the day of randomization) is analyzed with Cox's proportional hazards model. Proportional hazard assumption will be investigated using graphical diagnostics based on the Schoenfeld residuals. The results will be presented as the hazard ratio (HR) for LTOT 24h/day vs. 15h/day with 90% two-sided

confidence interval and the one-sided p-value for the hypothesis test if the lower limit exceeds 0.67 (see section 9.1) A two-sided p-value for the difference between treatments will also be presented. (OS table 10 and table 11). The ITT population will be used for primary analysis but all endpoints will be analyzed according to both the ITT and the Per Protocol (PP) principle.

Statistical significance is defined as a p-value < 0.05. As a sensitivity analysis, the primary analysis is repeated adjusting for sex and age at randomization in years. A frailty model will be performed with “center” as a random effect to account for the clustering by hospital.

Cases withdrawing from LTOT treatment are for the primary analysis handled as

- 1) Per protocol, if it is due to improved oxygenation.
- 2) Having reached endpoint, if it is due to adverse event (such as excessive nose bleeding etc.).
- 3) Censored, if it is due to cancellation of treatment for reasons other than treatment allocation or adverse events (such as starting to smoke etc.).

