Summary table of abbreviations and definitions used in this plan

AE	Adverse event
COPD	Chronic obstructive pulmonary disease
DV	Derived variables
EVF	Erythrocyte volume fraction
FEV ₁	Forced expired volume in one second
VC	Vital capacity
ITT	Intention-to-treat – all randomized patients who has started LTOT, regardless of adherence (see section 6.1 in this SAP)
IQR	The InterQuartile Range (the second and third quartiles, or the middle half of the data set)
kPa	Kilopascal
LPO	Last patient out
LTOT	Long-term oxygen therapy
OS	Output shells
PaO ₂	Partial pressure of arterial oxygen
PP	Per protocol – patients who fulfill certain criteria (see section 6.2 in this SAP)

R-RCT	Registry-based, randomized, controlled trial
SAE	Serious adverse event
Safety population	All randomized patients who have started LTOT. This includes incorrectly randomized patients.
SAP	Statistical analysis plan
SD	Standard deviation
SUSAR	Suspected unexpected serious adverse reaction
Swedevox	Swedish register for respiratory failure
UCR	Uppsala Clinical Research centre

4 Study objectives and outcome variables

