4.2.1 Primary outcome variable

All-cause mortality or 1st hospitalization 1 year after randomization.

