5.4.2 Registry-based follow-up

All 48 units prescribing and managing LTOT in Sweden report to the National Registry for Respiratory Failure (Swedevox). Data on patient characteristics and the prescribed oxygen therapy are obtained from Swedevox. The completeness of the baseline data will be checked using Swedevox and optimized through contacts with participating centers by the national Swedevox coordinator and by the Study Coordinator.

The main endpoints of mortality and hospitalizations are assessed using national Swedish governmental registries: date and causes of death (Causes of Death Register), and the date and diagnoses/procedural codes of hospitalizations (National Patient Register of in- and outpatient care). Data are cross-linked

between registers using each participant's unique Swedish identity number. In addition, data will be obtained on dispensed outpatient medications (Prescribed Drug Register). Endpoints are assessed at 3 and 12 months after randomization (study end).

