9.1 Limit of non-superiority and Hypotheses

A time-to-composite event survival analysis, with composite event equal to death or 1st hospitalization as endpoint, is used. The hypothesis of non-superiority of continuous oxygen is tested. The null hypothesis is rejected if the hazard ratio (HR) of continuous oxygen vs. 15h/day exceeds the limit 0.67. The use of oxygen is burdensome and with hospitalization, being less serious than death, incorporated into the primary endpoint, the HR of 0.67 was judged to be the appropriate limit for the composite primary outcome. This was the difference in mortality or hospitalization that the investigators judged to be clinically worthwhile. (See also section 10 Changes to the planned analysis.)

$H_0: HR_{24h/day} \leq 0.67$

$H_A: HR_{24h/day} > 0.67$ Continuous oxygen is not better than 15h/day;

If significance is obtained, the conclusion is that LTOT prescribed for 24 h/day does not reduce the rate of the composite event of all-cause death or 1st hospitalization at 1 year compared to LTOT prescribed for 15 h/day in patients starting LTOT for chronic respiratory failure.

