9.2 Sample size calculation

Calculation of the final required sample was based on a time-to-composite event survival model with the use of the Cox proportional hazards (PH) model and checked against the results of the log-rank test statistic. Assuming 80% power to verify a hazard ratio for death or 1st hospitalization of more than 0.67 in the 24h group vs. the 15h group, a one-sided type I error rate of 0.05, and an event rate of 80% based on Swedevox registry data, we calculated a total sample size of 189 patients with Cox PH and 181 using the log-rank statistic. Making allowances for a loss of patients in the PP analysis, the final planned total trial size is 230, with 1:1 allocation. No patient is expected to be lost to follow-up for the primary composite endpoint of death or 1st hospitalization in the ITT population, due to the use of national registries. The following R code for a Cox PH non-inferiority calculation, inverting the hypothesized hazard ratio from the non-superiority hypothesis for this study, was used for the sample size calculation:

#Hazard Ratio, hr

#Null-Hypothesis Hazard Ratio, hr0

#Overall Probability of Event, pE

#Proportion of Sample in Group 'A', pA

```
> hr=1
```

```
> hr0=1.5
```

```
> pE=0.8
```

```
> pA=0.5
```

```
> alpha=0.05 # 1-sided test
```

```
> beta=0.20
```

```
> (n=((qnorm(1-alpha)+qnorm(1-beta))/(log(hr)-log(hr0)))^2/(pA*(1-pA)*pE))
```

```
[1] 188.0317
```

```
> ceiling(n)
```

```
[1] 189
```

10 Changes to the planned analysis (2020-01-22)

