*Socialstyrelsen will provide us with the date of event. Time to event (in days) will be calculated by UCR

*Time to composite event (All-cause mortality/ All-cause Hospitalization)	Included in the order from Socialstyrelsen
*Time to all-cause mortality	Included in the order from Socialstyrelsen
*Time to 1st hospitalization	Included in the order from Socialstyrelsen
Mortality from respiratory disease	respiratory disease or infection (A40; J00-J99)
Mortality from cardiovascular disease	Underlying cause of death (UCD) heart disease (I00-I99)
Hospitalization from respiratory disease	UCD respiratory disease or infection (A40; J00-J99)
Hospitalization from cardiovascular disease	UCD heart disease (I00-I99)
Time to Mortality from respiratory disease	Death (from respiratory disease) date – Study start date
Time to Mortality from cardiovascular disease	Death (from cardiovascular disease) date – Study start date
Time to Hospitalization from respiratory disease	Date of hospitalization from respiratory disease – Study start date
Time to Hospitalization from cardiovascular disease	Date of hospitalization from cardiovascular disease – Study start date
Time from start until the patient stops being treated	End of treatment – Date for start of treatment
Discontinued LTOT	From Swedevox Registry
Withdrawals	DATE_OF_LTOT_WITHDRAWAL REASON_W
ITT	All randomized patients that start LTOT
PP	A randomized patient will be excluded from the PP set if LTOT has been discontinued before the primary outcome assessment or the mean LTOT utilization during follow-up to the primary endpoint is below 20 h/day for the 24 h/day group, and below 13 h/day or above 17 h/day in the LTOT 15 h/day group
COPD	J44; exacerbation: J44.0 and J44.1
Heart disease	I00-I99
Respiratory disease or infection	A40; J00-J99
fev1/fvc	FEV1/FVC
BMI	WEIGHT(kg)/(HEIGHT (m)*HEIGHT (m))
Age	Round down (RANDOMIZATION_DATE - DATE_OF_BIRTH)/365.25
Duration of treatment	Number of days with treatment during the study
Self-rated hours of oxygen	Self-reported oxygen use (mean hours/24h) is categorized using 1) average use since starting LTOT, or (if missing) mean h/day last week; using the

	questionnaire at 12 months, or (if missing) 3 months (and the described algorithm used for each time point).
Subgroup 1 Participants with more severe resting hypoxemia at LTOT start	PaO ₂ < 7.4 kPa breathing air
Subgroup 2 Participants with more moderate hypoxemia at LTOT start	PaO ₂ 7.4–8.0 kPa breathing air

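### SAP 7.5 counts stopping LTOT for an adverse event as a primary event and censors some other stops, against the SAP's own endpoint and ITT definition

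*SAP*

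**What the plan says.** SAP 7.5 makes ITT the population for the primary analysis. It then lists how patients who withdraw from LTOT are treated in that analysis:

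- Stopping because oxygenation improved is handled as per protocol.
- Stopping for an adverse event is handled as "Having reached endpoint, if it is due to adverse event (such as excessive nose bleeding etc".
- A third group is "Censored, if it is due to cancellation of treatment for reasons other than treatment allocation or adverse events", with starting to smoke as the example.

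Elsewhere the SAP describes a different event and a different kind of follow-up:

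- Section 4.2.1 gives the primary outcome as "All-cause mortality or 1st hospitalization 1 year after randomization".
- Section 5.4.2 gives the source: "The main endpoints of mortality and hospitalizations are assessed using national Swedish governmental registries".
- The Derived Variables appendix builds the primary variable as "Time to composite event (All-cause mortality/ All-cause Hospitalization"), with event dates supplied by the national authority. It has no withdrawal component.
- The definitions table in section 3 gives ITT as "all randomized patients who has started LTOT, regardless of adherence".
- Section 9.2 states: "No patient is expected to be lost to follow-up for the primary composite endpoint of death or 1st hospitalization in the ITT population".
- Section 9.1 says that a significant result means 24 h/day "does not reduce the rate of the composite event of all-cause death or 1st hospitalization at 1 year".

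**The concern.** A patient who stops LTOT because of nosebleeds, is not admitted and is alive at day 365 is an event under 7.5. The same patient is a non-event under 4.2.1, 9.1 and the Derived Variables appendix. A programmer working from the appendix and one working from 7.5 would build different primary datasets.

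The direction matters because the hypothesis is reversed from the usual one: the trial succeeds when the hazard ratio is shown to exceed 0.67. Events that 24 h/day does not reduce, or that it makes more frequent, pull a truly beneficial hazard ratio up toward that conclusion. The conclusion would still be worded as if only deaths and hospitalizations had been counted.

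The censoring rule is a separate difficulty. It discards deaths and admissions after LTOT has stopped, although the SAP expects the registers to lose nobody in the ITT set.

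**Working it through.** **The text.** Sections 4.2.1, 5.4.2, 9.1 and the Derived Variables appendix contain two event types, death and hospitalization. Section 7.5 adds a third. The list in 7.5 cannot be confined to the per-protocol analysis. It is stated for the primary analysis, which the same section makes ITT, and section 6.2 excludes patients who discontinued LTOT from the per-protocol set, so the rules would have little to act on there. The three rules also leave a gap: stopping because of the treatment allocation, without an adverse event, falls under none of them. The only sensitivity analyses listed in 7.5 are adjustment for sex and age and a center frailty model.

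**The plan's own figure.** The formula in 9.2 gives n = [(1.645 + 0.842)/(ln 1 − ln 1.5)]² / (0.25 × 0.8) = 188.03, so 189 as stated. It uses the 80% event rate for death or first hospitalization alone, so the adverse-event stops are not in the sample size.

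**Effect of the adverse-event rule.** From the SAP: margin 0.67, one-sided 5% test, 230 patients allocated 1:1, 80% events. Assumed, because the SAP gives none: the one-year risk of stopping LTOT for an adverse event in each arm. Also assumed: constant hazards.

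Let L be the 15 h hazard of death or hospitalization, and let a24 and a15 be the adverse-event withdrawal hazards, a = −ln(1 − risk). At a true hazard ratio of 0.67, the ratio actually analysed is

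HR = (0.67 L + a24) / (L + a15).

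This exceeds 0.67 whenever a24 > 0.67 × a15, so equal withdrawal in the two arms already moves it upward.

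The 80% can be read in two ways:

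- 80% in the 15 h arm: L = −ln 0.2 = 1.609, with 168 expected events at HR 0.67.
- 80% overall: L = 1.991 (86.3% and 73.7% by arm), with 184 expected events.

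Example, with 10% (24 h) and 5% (15 h) and L = 1.609:

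- a24 = 0.1054 and a15 = 0.0513.
- HR = (1.0783 + 0.1054)/(1.6094 + 0.0513) = 0.713.
- Expected events 172.9, so SE = 2/√172.9 = 0.152.
- Shift = ln(0.713/0.67)/0.152 = 0.41, and the error is Φ(0.41 − 1.645), about 10.8%.

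The table gives the analytic hazard ratio and the error from 20,000 simulated trials per scenario (exponential times, 115 per arm, Cox model). In each cell the first value is for 80% in the 15 h arm and the second for 80% overall.

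| Assumed risk 24 h / 15 h | HR analysed | One-sided error |
|---|---|---|
| none | 0.670 | 5.15% / 5.21% |
| 5% / 5% | 0.680 / 0.678 | 6.17% / 6.04% |
| 10% / 10% | 0.690 / 0.687 | 7.55% / 7.22% |
| 4% / 2% | 0.687 / 0.684 | 7.11% / 6.75% |
| 10% / 5% | 0.713 / 0.705 | 10.97% / 9.91% |
| 20% / 5% | 0.784 / 0.762 | 27.4% / 23.0% |
| 3% / 5% | 0.668 / 0.668 | 4.82% / 4.91% |
| 5% / 10% | 0.659 / 0.661 | 4.06% / 4.08% |

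**Effect of the censoring rule.** If 10% in each arm are censored at random, the hazard ratio stays at 0.67 and the error at 5.2%. Mean events fall from 184 to 177, or from 168 to 161. If stopping is related to prognosis, the censoring is informative, and the document does not determine the direction of the bias.

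**The case against.** The best counter-argument is that 7.5 is explicit and more specific than the general endpoint definition, so an analyst would follow it, and that counting an adverse-event stop as failure is a recognised composite strategy. The error figures above are also relative to the hazard ratio for death or hospitalization. For the event that 7.5 actually codes, the test keeps its nominal level. Both points are fair. But a composite strategy then belongs in the outcome definition, the derived variable and the conclusion, and it is in none of them. Sections 9.1 and 10 also justify the 0.67 margin for death or first hospitalization only.

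Other points and what stands of them:

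- The rules remove nobody from the ITT set. True. The conflict is that event status and follow-up time come to depend on adherence, which the definition says should not matter.
- The shell for Table 5.19 already has a 12-month ITT row for the composite with a hazard ratio. It carries a 95% interval, is not tied to the 0.67 test, and does not say that the withdrawal rules are switched off.
- A footnote to the CONSORT chart says register data are available except for withdrawals. Section 3 and Table 1 keep study withdrawal apart from LTOT discontinuation, so the footnote does not show that register data are lost when a patient merely stops oxygen.
- The SAP seems to expect few adverse-event data (7.8 and Table 12.1), and stops that lead to admission are events anyway. This argues for the lower rows of assumed risk. The 20%/5% case has no basis in the document beyond showing the range.

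**Conclusion.** The plan is wrong as written. The primary ITT analysis would count an event that the primary outcome, the derived variable and the stated conclusion all leave out, and it would stop follow-up that the SAP says can be completed. That rests on the text alone.

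The size is conditional, because withdrawal rates are not given and constant hazards are assumed. Low rates, or rates weighted to the 15 h arm, do little: the error ranges from about 4% to about 6% for the 3%/5%, 5%/10% and 5%/5% cases. Rates weighted to the 24 h arm can double the error (10–11% at 10%/5%) or more. The censoring rule costs about 7 events at 10% random censoring; any bias from it is undetermined. An unclear primary event in a confirmatory one-sided test should be settled before unblinding.

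**What to change.** Reconcile section 3 (ITT), 4.2.1, 7.5 and the Derived Variables appendix. Suggested text for 7.5: *The primary ITT analysis is time from randomization to register-recorded all-cause death or first hospitalization through day 365, whatever the LTOT status. Follow-up is censored only at day 365 or when register follow-up truly ends.*

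If the present withdrawal rules are wanted, keep them as a labelled sensitivity analysis and say there how stopping because of treatment allocation is handled. At the same time, square the first rule with 6.2: it treats stopping for improved oxygenation as per protocol, whereas 6.2 excludes discontinued patients from the per-protocol set.

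The cost is a few lines in the SAP, and a change to protocol version 1.8 (not available for this review) if it carries the same rules. The calculated 189 and planned 230 stand, since both rest on death or first hospitalization alone. Register follow-up for the endpoint and by-arm reporting of discontinuations (7.4, Table 1) are already planned.

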7.6 Analysis of secondary variables

Hospitalizations are analyzed using Fine Gray regression [ref 1,2,3] accounting for death as competing event. All-cause mortality will be analyzed as the secondary outcome. Number of competing events will be presented for each analysis. Other secondary endpoints are analyzed using two-sided Student's t-tests for continuous variables (including HRQOL, breathlessness, cognition, fatigue, activity, and health care usage) and chi-2 test for categorical variables (causes of death, cognition, treatment preference). Correlational analyses, including of factors predictive of the primary and secondary outcomes will be conducted using linear regression (continuous outcomes), logistic regression (categorical outcomes), and Cox and Fine-Gray regression models (time to event outcomes).

All analyses are subject to underlying conditions – if not fulfilled due to e.g. a too small sample, it will not be attempted. Analyses of secondary variables other than the ones underlined in section 4.2.2 will be performed at Region Blekinge.

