4.1.2 Secondary objectives

Compared to patients with LTOT prescribed for 15 h/day, does continuous oxygen therapy 24 h/day: (underlined objectives will be analyzed and reported by UCR)

- Fail to reduce the mortality rate from all causes?
- Fail to reduce hospitalization rate from all causes?
- Fail to reduce mortality rate from respiratory disease?
- Fail to reduce mortality rate from cardiovascular disease?
- Fail to reduce hospitalization rate from respiratory disease?
- Fail to reduce hospitalization rate from cardiovascular disease?
- Fail to reduce the rate of an incident diagnosis of cardiovascular disease?
- Fail to reduce the level of breathlessness?
- Fail to reduce fatigue?
- Fail to improve level of self-reported physical activity?
- Fail to improve health-related quality of life (HRQOL)?
- Fail to improve cognition?
- Fail to increase the self-reported oxygen utilization?
- Fail to decrease the rate of LTOT withdrawal?
- Fail to increase the patient's preference in continuing LTOT?

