4.2.2 Secondary outcome variables

- Mortality rate from all causes at 3 and 12 months
- Mortality rate from respiratory disease at 3 and 12 months
- Mortality rate from cardiovascular disease at 3 and 12 months
- Hospitalization rate from all causes at 3 and 12 months
- Hospitalization rate with a primary diagnosis of respiratory disease or respiratory infection at 3 and 12 months
- Hospitalization rate with a primary diagnosis of cardiovascular disease at 3 and 12 months
- Rate of an incident diagnosis of cardiovascular disease at 3 and 12 months

Self-reported questionnaire data collected at 3 and 12 months:

- Self-rated oxygen utilization
- Breathlessness (Multidimensional Dyspnea Profile; MDP)
- Fatigue (FACIT-Fatigue)
- Informant-rated cognition (IQCODE and FAQ)
- Self-rated cognition (BAS)
- Health-related quality of life (CAT and EQ5D-5L)
- Global impression of change from baseline (GIC)
- Self-reported physical activity
- Preference of continuing treatment

5 Study design

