	Event rate per 100 patient-years (95% CI)	xx.x	xx.x	xx.x
	HR (95% CI) - p-value	xx.x (x.xx-x.xx) – 0.xxxx		
All-cause Hospitalization	Number of patients	xx	xx	xx
	Number of events	xx	xx	xx
	Number of competing events	xx	xx	xx
	Person-years	xxx	xxx	xxx
	Events/Participants	xx.x	xx.x	xx.x
	Event rate per 100 patient-years (95% CI)	xx.x	xx.x	xx.x
All-cause mortality	Number of patients	xx	xx	xx
	Number of events	xx	xx	xx
	Person-years	xxx	xxx	xxx
	Events/Participants	xx.x	xx.x	xx.x
	Event rate per 100 patient-years (95% CI)	xx.x	xx.x	xx.x
	HR (95% CI) - p-value	xx.x (x.xx-x.xx) – 0.xxxx		
Mortality from respiratory disease	Number of patients	xx	xx	xx
	Number of events	xx	xx	xx
	Person-years	xxx	xxx	xxx
	Events/Participants	xx.x	xx.x	xx.x
	Event rate per 100 patient-years (95% CI)	xx.x	xx.x	xx.x
	HR (95% CI) - p-value	xx.x (x.xx-x.xx) – 0.xxxx		
Mortality from cardiovascular disease	Number of patients	xx	xx	xx
	Number of events	xx	xx	xx
	Person-years	xxx	xxx	xxx

	Statistics	LTOT 24h/day	LTOT 15h/day	Total
	Events/Participants	xx.x	xx.x	xx.x
	Event rate per 100 patient-years (95% CI)	xx.x	xx.x	xx.x
	HR (95% CI) - p-value	xx.x (x.xx-x.xx) – 0.xxxx		
Hospitalization from respiratory disease	Number of patients	xx	xx	xx
	Number of events	xx	xx	xx
	Number of competing events	xx	xx	xx
	Person-years	xxx	xxx	xxx
	Events/Participants	xx.x	xx.x	xx.x
	Event rate per 100 patient-years (95% CI)	xx.x	xx.x	xx.x
	HR (95% CI) - p-value	xx.x (x.xx-x.xx) – 0.xxxx		
Hospitalization from cardiovascular disease	Number of patients	xx	xx	xx
	Number of events	xx	xx	xx
	Number of competing events	xx	xx	xx
	Person-years	xxx	xxx	xxx
	Events/Participants	xx.x	xx.x	xx.x
	Event rate per 100 patient-years (95% CI)	xx.x	xx.x	xx.x
	HR (95% CI) - p-value	xx.x (x.xx-x.xx) – 0.xxxx		

- Table 5.14 Event rate at 3 months (PP)
- Table 5.15 Event rate at 3 months (Subgroup 1)
- Table 5.16 Event rate at 3 months (Subgroup 2)
- Table 5.17 Event rate at 3 months (Subgroup 3)
- Table 5.18 Event rate at 3 months (Subgroup 4)
- Table 5.19 Event rate at 12 months (ITT)
- Table 5.20 Event rate at 12 months (PP)
- Table 5.21 Event rate at 12 months (Subgroup 1)
- Table 5.22 Event rate at 12 months (Subgroup 2)
- Table 5.23 Event rate at 12 months (Subgroup 3)
- Table 5.24 Event rate at 12 months (Subgroup 4)

Table 6 Demographics and characteristics at baseline

Table 6.1 ITT

Variable	Statistics	LTOT 24h/day n	LTOT 15h/day n	Total n	*P-value
Age (years)	n	x	x	x	0.xxx
	Mean (SD)	x (x)	x (x)	x (x)	

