	All-cause mortality	LTOT 15h/day	xx	x.xx (x.xx-x.xx)	x.xx	x.xxx
	All-cause Hospitalization***	LTOT 15h/day	xx/xx	x.xx (x.xx-x.xx)	x.xx	x.xxx
	Mortality from respiratory disease	LTOT 15h/day	xx	x.xx (x.xx-x.xx)	x.xx	x.xxx
	Mortality from cardiovascular disease	LTOT 15h/day	xx	x.xx (x.xx-x.xx)	x.xx	x.xxx
	Hospitalization from respiratory disease***	LTOT 15h/day	xx/xx	x.xx (x.xx-x.xx)	x.xx	x.xxx
	Hospitalization from cardiovascular disease***	LTOT 15h/day	xx/xx	x.xx (x.xx-x.xx)	x.xx	x.xxx
At 1 year	All-cause mortality	LTOT 15h/day	xx	x.xx (x.xx-x.xx)	x.xx	x.xxx
	All-cause Hospitalization ***	LTOT 15h/day	xx/xx	x.xx (x.xx-x.xx)	x.xx	x.xxx
	Mortality from respiratory disease	LTOT 15h/day	xx	x.xx (x.xx-x.xx)	x.xx	x.xxx

	Mortality from cardiovascular disease	LTOT 15h/day	xx/xx	x.xx (x.xx-x.xx)	x.xx	x.xxx
	Hospitalization from respiratory disease***	LTOT 15h/day	xx/xx	x.xx (x.xx-x.xx)	x.xx	x.xxx
	Hospitalization from cardiovascular disease***	LTOT 15h/day	xx	x.xx (x.xx-x.xx)	x.xx	x.xxx

*** Hospitalizations are analyzed using Fine Gray regression accounting for death as competing event

Table 11.2 Secondary outcome (PP)

Table 11.3 Secondary outcome (Subgroup 1)

Table 11.4 Secondary outcome (Subgroup 2)

Table 11.5 Secondary outcome (Subgroup 3)

Table 11.6 Secondary outcome (Subgroup 4)

Table 11.7 Analysis of Self-reported hours of oxygen

Similar table as in 10.1

	Population	Outcome	Mean difference (95% CI)	p-value**
At 3 months	ITT	Self-reported hours of oxygen* (within 24 hours)	x.xx (x.xx-x.xx)	x.xx
	PP	Self-reported hours of oxygen* (within 24 hours)	x.xx (x.xx-x.xx)	x.xx
	Subgroup 1	Self-reported hours of oxygen* (within 24 hours)	x.xx (x.xx-x.xx)	x.xx
	Subgroup 2	Self-reported hours of oxygen* (within 24 hours)	x.xx (x.xx-x.xx)	x.xx
	Subgroup 3	Self-reported hours of oxygen* (within 24 hours)	x.xx (x.xx-x.xx)	x.xx
	Subgroup 4	Self-reported hours of oxygen* (within 24 hours)	x.xx (x.xx-x.xx)	x.xx
At 1 year	ITT	Self-reported hours of oxygen* (within 24 hours)	x.xx (x.xx-x.xx)	x.xx
	PP	Self-reported hours of oxygen* (within 24 hours)	x.xx (x.xx-x.xx)	x.xx
	Subgroup 1	Self-reported hours of oxygen* (within 24 hours)	x.xx (x.xx-x.xx)	x.xx
	Subgroup 2	Self-reported hours of oxygen* (within 24 hours)	x.xx (x.xx-x.xx)	x.xx
	Subgroup 3	Self-reported hours of oxygen* (within 24 hours)	x.xx (x.xx-x.xx)	x.xx
	Subgroup 4	Self-reported hours of oxygen* (within 24 hours)	x.xx (x.xx-x.xx)	x.xx

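### The hospitalization-rate objectives are tested only with Fine-Gray, whose HR drifts modestly toward failure to reduce if 24 h/day improves survival; a cause-specific HR should be added beside it

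*SAP*

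**What the plan says.** Section 4.1.2 asks whether 24 h/day, compared with 15 h/day, would "Fail to reduce hospitalization rate from all causes", with parallel questions for respiratory and cardiovascular admissions. Section 4.2.2 lists the outcome as "Hospitalization rate from all causes at 3 and 12 months".

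For the analysis, section 7.6 says "Hospitalizations are analyzed using Fine Gray regression [ref 1,2,3] accounting for death as competing event", and the footnote to output Table 11.1 repeats it: "Hospitalizations are analyzed using Fine Gray regression accounting for death as competing event". Cox is named in 7.6 only within the correlational and predictor analyses ("logistic regression (categorical outcomes), and Cox and Fine-Gray regression models (time to event outcomes"), so no cause-specific model is planned for the treatment comparison of hospitalizations.

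Section 7.6 also plans related information: "All-cause mortality will be analyzed as the secondary outcome" and "Number of competing events will be presented for each analysis". For every outcome, Table 5.13 lists person-years and a row "Event rate per 100 patient-years (95% CI". Its respiratory and cardiovascular hospitalization blocks also carry an HR row, without naming the model; its all-cause hospitalization block has none.

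Table 11.1 gives each secondary outcome a 90% CI and two p-value columns. The marks on those columns are explained under Table 10.1, where the second is the one-sided test against 0.67. The note to Figure 5 extends the non-superiority display to all secondary endpoints.

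**The concern.** Fine-Gray compares subdistribution hazards: patients who die before any admission stay in the risk set as never admitted. Its HR therefore depends on the effect on death as well as on the admission rate among patients still alive and not yet admitted. In a trial designed to show superiority, a shift toward 1 is usually cautious. Here the conclusion sought is that 24 h/day does not reduce admissions, so a shift toward 1 is in the favourable direction.

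If 24 h/day lowers mortality, more patients live long enough to be admitted and the Fine-Gray HR rises above the rate ratio. If it raises mortality, the HR falls and can resemble a benefit on admissions. This arises even when only first admissions are counted. At stake is how the three hospitalization objectives are read. An HR under person-time rates also invites the reader to take it as the ratio of those rates, which a Fine-Gray HR is not.

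**Working it through.** **The plan's own figure (section 9.2).** N = (z₀.₉₅ + z₀.₈₀)² / [(ln 1.5)² × 0.5 × 0.5 × 0.8] = 188.03, rounded up to 189. This reproduces the SAP. It concerns the composite; the SAP sizes no hospitalization outcome.

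**Inputs from the SAP.** 230 patients, 1:1 (115 per arm); one-year composite event rate 80%, applied here to the 15 h/day arm; limit 0.67; one-sided 5%; registry follow-up taken as complete to day 365. A death HR of 0.83 is used because section 10 records it as the mortality limit of the original design.

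**Assumed, not in the SAP.** Constant hazards; the share *s* of first events that are deaths without prior admission (5–30%); death HRs of 0.67 and 0.50 besides 0.83.

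**Method.** With complete one-year follow-up, Fine-Gray equals a Cox model in which patients who died stay at risk to day 365.
- Total control hazard: λ = −ln(1 − 0.80) = 1.609 per year. Admission λ₁ = (1 − s)λ; death λ₂ = sλ.
- Cumulative incidence of admission: F = [λ₁/(λ₁ + λ₂)] × [1 − exp(−(λ₁ + λ₂))].
- The large-sample Fine-Gray HR (sHR) is the root of the Cox score equation with 1 − F(t) as the risk-set proportion in each arm.
- Chance that the lower 90% limit exceeds 0.67: Φ{ln(sHR/0.67) × √(D/4) − 1.645}, with D = 115 × (F₁₅ + F₂₄).

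**One case in full (s = 20%, admission ratio 0.67, death HR 0.67).**
- 15 h/day: λ₁ = 1.288, λ₂ = 0.322, F = 0.80 × 0.80 = 0.640.
- 24 h/day: λ₁ = 0.863, λ₂ = 0.216, F = 0.80 × [1 − exp(−1.078)] = 0.528.
- sHR = 0.722; D = 115 × 1.168 ≈ 134.
- Φ{0.075 × 5.79 − 1.645} = 0.113.

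**All-cause admission, true rate ratio 0.67: sHR (chance of declaring non-superiority)**

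| Death HR | s = 5% | s = 10% | s = 20% | s = 30% |
|---|---|---|---|---|
| 1.00 | 0.676 (5.6%) | 0.680 (6.0%) | 0.685 (6.4%) | 0.687 (6.6%) |
| 0.83 | 0.681 (6.1%) | 0.689 (7.1%) | 0.704 (8.6%) | 0.714 (9.7%) |
| 0.67 | 0.685 (6.7%) | 0.699 (8.3%) | 0.722 (11.3%) | 0.741 (13.6%) |
| 0.50 | 0.690 (7.3%) | 0.709 (9.8%) | 0.743 (14.8%) | 0.772 (19.2%) |

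A cause-specific Cox model censored at death targets 0.67 in every cell and holds the error at 5% (4–6% when simulated). The first row shows that part of the shift is present with no survival effect.

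**Larger true reductions.** At a true ratio of 0.60 the Fine-Gray chance is 1.2–7.3% (Cox 1.0–1.3%). At 0.50 it is below 1% in every case.

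**Respiratory and cardiovascular admissions.** Assuming a one-year net admission risk of 15% or 50% with a net death risk of 35%, or 50% with 20%, a true ratio of 0.67 and death HRs of 0.83 to 0.50 give an sHR of 0.69–0.75 and an error of 6.0–13.7%.

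**Opposite direction.** With an admission ratio of 1.0 and a death HR of 1.5, the Fine-Gray HR is 0.95, 0.93 and 0.91 for control one-year admission-first/death-first risks of 70/10, 65/15 and 60/20%.

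**The case against.** The best reply is that the plan may not intend an instantaneous rate. Section 9.2 calls 80% an event rate and its code labels the same number a probability; section 4.2.2 fixes the rate at 3 and 12 months; Table 9.1 reports n (%). On that reading the target is cumulative incidence, which Fine-Gray addresses, and the choice between the two hazards is a choice of estimand. This stands in part. The SAP never says which is meant, while Table 5.13 gives person-time rates for the same outcomes. It is a reason to keep Fine-Gray, not to leave the rate question without a cause-specific estimate.

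Second, a mortality difference would not be hidden. The all-cause mortality HR, competing-event counts and arm-level rates are all reported, and the primary Cox model counts death and admission together, so a treatment that reduced both would be picked up there. This stands and limits the consequence. It alerts the reader but does not correct the hospitalization test.

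Third, the size rests on assumed inputs and is largest at the limit itself. This also stands. At the SAP's own mortality figure of 0.83 the error is about 6–10%, and it shrinks quickly as the true reduction grows. The 0.67 limit was argued for the composite only, although the output shells carry it to the secondary endpoints.

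Finally, Table 5.13 does not set a Fine-Gray HR beside the all-cause hospitalization rates. That block has no HR row, the model for the other two is not named, and person-years are not defined. Any mismatch there depends on how those rows are filled.

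**Conclusion.** The point holds as a modest, directional weakness in three secondary outcomes. The only planned test of the hospitalization-rate objectives is one whose HR moves with mortality, and a survival benefit moves it toward the conclusion the trial is set up to draw. With a true ratio of 0.67, the HR is about 0.68–0.71, 0.69–0.74 and 0.69–0.77 for death HRs of 0.83, 0.67 and 0.50. The corresponding error is about 6–10%, 7–14% and 7–19% against a nominal 5%. These figures assume constant hazards and a death-first share of 5–30%, which the SAP does not give.

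A reader might infer that a survival benefit would turn a real reduction in admissions into a finding of no reduction, or that Fine-Gray is the wrong model. The documents support neither. The false conclusion has at most about a 19% chance at the limit, about 7% at a true ratio of 0.60 and less than 1% at 0.50. Fine-Gray is valid for cumulative incidence, and the primary composite is unaffected.

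**What to change.** In section 7.6 and Table 11.1, and in the HR rows of Table 5.13, add for each hospitalization outcome a cause-specific Cox HR for 24 h vs 15 h/day: first admission of that type as the event, follow-up censored at death. State that the hospitalization-rate objectives are read from this HR, because it corresponds to the person-time rates shown. Keep the Fine-Gray HR, labelled as the effect on cumulative incidence, and print both beside the mortality HR.

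The cost is SAP wording, one extra model and one extra HR column per hospitalization outcome, using registry dates already ordered. No patients or data are added. The small downside is a second HR to explain. Dropping Fine-Gray would be a real trade-off and is not needed.
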